#### 6.10 Prior and Concomitant Medications

All medications, prescription and over-the-counter (OTC), administered or taken by the subject during the study are to be recorded on the concomitant medication form of the CRF. Information should be recorded for: name of drug, dose, route of administration, start and end dates, and indication.

Any therapeutic or surgical procedure performed for concurrent conditions through the end of the study, should be recorded, including the date, description of the procedure, and clinical findings.

#### 6.11 Prohibited Concomitant Medications/Therapies

Investigational drugs or therapies should not be used at any time during the study because of their potential to confound the results. The following drugs or therapies are prohibited during the study because of their potential to confound the results:

- Application of prescription or OTC topical drug products (including but not limited to: gel, patch, cream, ointment, lotion, or spray) to the study drug application site(s), i.e., on the breast(s).
- Prescription or OTC treatments that are known/suggested to have an estrogenic or antiandrogenic effect including SERMs and aromatase inhibitors.

#### 7.0 STUDY PROCEDURES

#### 7.1 Screening (Within 30 days prior to randomization)

Subjects who fulfill the Inclusion and Exclusion criteria and who have signed an Informed Consent Form will receive a Physical Examination including a breast exam. Relevant medical history will be recorded. Subjects will also be asked to complete a questionnaire on their menstrual cycle as shown in Appendix 3. Measurements of vital signs, including height and weight and laboratory measurements including hematology, blood chemistry, and hormones will be performed. A urine pregnancy test will be performed on women of child bearing potential. A bilateral mammogram with both the raw and processed 2D image DICOM files needs to be performed within 3 months prior to randomization. The same (make/model/serial number) mammography machine must be used for the Week 52 mammogram and if the subject is participating in the Open-Label phase, the Week 104 mammogram. If the mammogram is older than 3 months but less than 18 months, or it cannot be provided in the format required for the study, the mammogram can be repeated to meet the study entry requirement after informed consent has been obtained.

# 7.2 Study Day 1 (Week 1): Baseline

Prior to dosing, the Inclusion/Exclusion criteria and Informed Consent will be reaffirmed with each subject.

Any changes that are found since the Screening Visit will be evaluated for an update to medical history and a focused Physical Examination will be performed at the Investigator's discretion. Measurements of vital signs, including weight and laboratory measurements including hematology, blood chemistry, coagulation factors, hormones, and bone biomarkers will be performed. A urine pregnancy test will be performed on women of child bearing potential.

Subjects will be stratified into pre/peri or post-menopausal groups and will be randomized to receive either 8mg/day (4mg/breast) BHR-700 gel or placebo. Each subject will be given a non-aerosol canister with a 1mL fixed dose pump. The subject will apply two (2) actuations ("squirts") of gel containing either: 2mg 4-OHT per 1 mL or placebo for daily application to each breast. The first dose will be applied under the supervision of the PI or designee.

A study drug kit, containing 6 canisters of study treatment, which is sufficient for 13 weeks of dosing, will be dispensed to each subject and a diary will be provided to capture dosing compliance. Subjects will be advised to call the clinic in between scheduled telephone calls and clinic visits if they experience AEs. Additional canisters may be assigned to avoid missing a dose due to lost or damaged canisters.

## 7.3 Blinded Phase Visits

• Study Week 1: Telephone Call (+/- 1 day)

During this visit, the site will call the subject and review the subject's dosing compliance, product application, and query for any AEs.

## • Study Week 4: Telephone Call (+/- 1 day)

During this visit, the site will call the subject and review the subject's dosing compliance, product application, and query for any AEs.

# • Study Week 8: Telephone call (+/- 1 day)

During this visit, the site will call the subject and review the subject's dosing compliance, product application and query for any AEs.

# • Study Week 13: (+/- 2 weeks)

Subjects will return to the clinic for study assessments. Vital signs including weight will be measured and the use of any concomitant medications and AEs recorded. A blood sample for PK measurements of 4-OHT isomers E and Z will be taken. A urine pregnancy test will be performed on women of child bearing potential. Treatment canisters will be weighed and the diary checked for study compliance. Treatment canisters, sufficient for 13 weeks dosing, will be dispensed.

# • Study Week 19: Telephone Call (+/- 2 weeks)

During this visit, the site will call the subject and review the subject's dosing compliance, product application, and query for any AEs.

## • Study Week 26: (+/- 2 weeks)

Subjects will return to the clinic for study assessments. Vital signs including weight will be measured and the use of any concomitant medications and AEs recorded. Laboratory measurements will be performed and will include hematology, blood chemistry, and coagulation factors. A blood sample for PK measurements of 4-OHT isomers E and Z will be taken. A urine pregnancy test will be performed on women of child bearing potential. Treatment canisters will be weighed and the diary checked for study compliance. Treatment canisters, sufficient for 13 weeks dosing, will be dispensed.

## • Study Week 32: Telephone Call (+/- 2 weeks)

During this visit, the site will call the subject and review the subject's dosing compliance, product application, and query for any AEs.

## • Study Week 39: (+/- 2 weeks)

Subjects will return to the clinic for study assessments. Vital signs including weight will be measured and the use of any concomitant medications and AEs recorded. A urine pregnancy test will be performed on women of child bearing potential. Treatment canisters will be weighed and the diary checked for study compliance. Treatment canisters, sufficient for 13 weeks dosing, will be dispensed.

# • Study Week 45: Telephone Call (+/- 2 weeks)

During this visit, the site will call the subject and review the subject's dosing compliance, product application, and query for any AEs.

• Study Week 52: (+/- 2 weeks) – End of Blinded Phase and End of Study Visit

Subjects will return to the clinic for study assessments. A Physical Examination including a breast exam will be performed, vital signs, height and weight will be measured and AEs and the use of any concomitant medications will be recorded. Laboratory measurements will be performed and will include hematology, blood chemistry, coagulation factors, hormones and bone biomarkers. PK measurements of 4-OHT isomers E and Z will be taken. A urine pregnancy test will be performed on women of child bearing potential. Treatment canisters will be weighed and the diary checked for study compliance. A mammogram will be performed.

Subjects will be offered the opportunity to participate in the Open-Label-Extension Phase of the study. Informed consent will be obtained from those subjects choosing to continue in the Open-Label-Extension Phase. Open-labeled study drug will be dispensed to those subjects who have agreed to administer the BHR-700 gel for an additional 52 weeks.

## 7.4 Open-Label Phase Visits

• Study Week 1 (53): Telephone call (+/- 1 day)

During this visit, the site will call the subject and review the subject's dosing compliance, product application, and query for any AEs.

• Study Week 4 (56): Telephone Call (+/- 1 day)

During this visit, the site will call the subject and review the subject's dosing compliance, product application, and query for any AEs.

## • Study Week 8 (60): Telephone call (+/- 1 day)

During this visit, the site will call the subject and review the subject's dosing compliance, product application, and query for any AEs.

• Study Week 13 (65): (+/- 2 weeks)

Subjects will return to the clinic for study assessments. Vital signs including weight will be measured and the use of any concomitant medications and AEs recorded. A urine pregnancy test will be performed on women of child bearing potential. Treatment canisters will be weighed and the diary checked for study compliance. Treatment canisters, sufficient for 13 weeks dosing, will be dispensed.

• Study Week 19 (71): Telephone Call (+/- 2 weeks)

During this visit, the site will call the subject and review the subject's dosing compliance, product application, and query for any AEs.

• Study Week 26 (78): (+/- 2 weeks)

Subjects will return to the clinic for study assessments. Vital signs including weight will be measured and the use of any concomitant medications and AEs recorded. Laboratory measurements will be performed and will include hematology, blood chemistry, and coagulation factors. A blood sample for PK measurements of 4-OHT isomers E and Z will be taken. A urine pregnancy test will be performed on women of child bearing potential. Treatment canisters will be weighed and the diary checked for study compliance. Treatment canisters, sufficient for 13 weeks dosing, will be dispensed.

• Study Week 32 (84): Telephone Call (+/- 2 weeks)

During this visit, the site will call the subject and review the subject's dosing compliance, product application, and query for any AEs.

• Study Week 39 (91): (+/- 2 weeks)

Subjects will return to the clinic for study assessments. Vital signs including weight will be measured and the use of any concomitant medications and AEs recorded. A urine pregnancy test will be performed on women of child bearing potential. Treatment canisters will be weighed and the diary checked for study compliance. Treatment canisters, sufficient for 13 weeks dosing, will be dispensed.

## • Study Week 45 (97): Telephone Call (+/- 2 weeks)

During this visit, the site will call the subject and review the subject's dosing compliance, product application, and query for any AEs.

# • Study Week 52 (104): (+/- 2 weeks) End of Open-Label Phase and End of Study Visit

Subjects will return to the clinic for study assessments. A Physical Examination including a breast exam will be performed, vital signs, height and weight will be measured and AEs and the use of any concomitant medications will be recorded. Laboratory measurements will be performed and will include hematology, blood chemistry, coagulation factors, hormones, and bone biomarkers. PK measurements of 4-OHT isomers E and Z will be taken. A urine pregnancy test will be performed on women of child bearing potential. Treatment canisters will be weighed and the diary checked for study compliance. A mammogram will be performed.

#### 8.0 ASSESSMENTS OF SAFETY

#### 8.1 Adverse Event Collection and Reporting

#### • Adverse Event Collection

AEs will be captured for the duration of the study. The reporting period begins with the first dose of study drug (Study Day 1) and ends at Week 52 and Week 104. The Adverse Events eCRF must be completed for all reported AEs and SAEs.

For this study, an AE is defined as: "Any untoward medical occurrence in a patient or clinical investigation subject administered a pharmaceutical product and which does not necessarily have a causal relationship with this treatment." This includes any newly occurring event or previous condition that has increased in severity or frequency since the administration of study drug.

AEs may also be reported spontaneously at any time. Details of any adverse or unexpected events, signs, and symptoms will be collected including details of onset, resolution, frequency, severity (as defined below), seriousness, relationship to the drug, effect on the study drug, treatments administered, and outcome. Any AE will be followed, whenever possible, until it returns to the baseline condition or becomes stable with no further change expected.

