## 6.7 Pregnancy and Nursing

The effects of 4-OHT gel on the developing human fetus at the recommended dose and route are unknown. For this reason, women of childbearing potential must agree to avoid pregnancy by using a reliable medically acceptable contraceptive method.

A woman is not considered to be of child bearing potential if she has:

- a. Serum follicle-stimulating hormone (FSH) levels consistent with menopause and has had complete amenorrhea for at least 12 months prior to starting drug.
- b. Documented surgical history of hysterectomy or bilateral oophorectomy/salpingo-oophorectomy.

A woman of child bearing potential must use one of the following contraceptive methods throughout the study and for at least 90 days after completing the study:

- a. Bilateral tube ligation performed 6 months or more prior to starting study drug.
- b. Consistent monogamous relationship with a male partner who has had a medically proven vasectomy performed 6 months or more prior to starting study drug.
- c. Intrauterine device (IUD) in place for at least 3 months before starting study drug.
- d. Progestin-containing hormonal birth control (oral, transdermal, injectable, or implantable) used consistently and successfully for at least 3 months prior to starting study drug.
- e. Double barrier contraception with spermicide, including a condom plus diaphragm or cervical cap. **Note:** Female condom should be used with male condom (as a double barrier method of contraception) due to risk of tearing.
- f. Abstinence

True abstinence, when this is in line with the preferred and usual lifestyle of the subject, is acceptable. Periodic abstinence (e.g., calendar, ovulation, symptothermal, post-ovulation methods) and withdrawal are not acceptable methods of contraception.

There is an unknown but potential risk for AEs in nursing infants secondary to treatment of the mother with 4-OHT gel. Therefore, it is required that breastfeeding be discontinued prior to the mother enrolling in this study (see also 5.2, exclusion criterion 4).

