## **Procedure for Reporting Pregnancy Exposure and Birth Events**

Should a female subject become pregnant or be suspected of being pregnant while participating in this study, the event must be reported to the Medical Monitor upon receipt of information by the study staff. While the pregnancy itself is not considered to be an AE or SAE, any pregnancy complications should be recorded as AEs or SAEs (if applicable). Any pregnancy will be followed through delivery for the observation of any SAEs. Fatalities and spontaneous abortions must be reported as SAEs.

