## 8.4 Serious Adverse Events

An SAE is any untoward medical occurrence that:

- Results in death.
- Is life-threatening. Life-threatening, in the definition of serious, refers to an event in which the subject was at risk of death at the time of the event; it does not refer to an event which hypothetically might have caused death if it were more severe.
- Requires hospitalization (> 24 hours) or prolongation of existing hospitalization.
- Results in persistent or significant disability/incapacity.
- Is a congenital anomaly/birth defect.

BHR-700 (0.2% 4-Hydroxytamoxifen (4-OHT) Gel) BHR PHARMA, LLC

[figure not shown]
• Is considered medically significant by the Investigator or requires intervention to prevent any one of the outcomes above. Medically significant are those events considered important in the Investigator's opinion that may not be immediately life-threatening or result in death or hospitalization but may jeopardize the subject or may require intervention to prevent one of the other outcomes listed in the definition above. These will also usually be considered serious.

All SAEs will be captured for the duration of the study. The reporting period begins with the first dose of study drug (Study Day 1) and ends at Week 52 and Week 104. All SAEs should be monitored until they are resolved or are clearly determined to be due to a subject's stable or chronic condition or intermittent illness.

Cause of death is required whenever known. If an autopsy was performed, an autopsy report should be provided. Death should usually be reported as the outcome of a specific SAE. Reports for hospitalization of elective procedures do not need to be reported as SAEs if there are no precipitating signs/symptoms or worsening of a pre-existing condition that necessitated the procedure. However, SAEs must be reported for any complications resulting from a procedure that prolonged the hospitalization.

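### Pregnancy reporting is required only during study participation although contraception is required for at least 90 days longer, and no contact after the final visit asks about pregnancy or new serious events

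*Protocol*

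**What the plan says.** Protocol Section 8.1 sets the window for adverse events: "The reporting period begins with the first dose of study drug (Study Day 1) and ends at Week 52 and Week 104". Section 8.4 states "All SAEs will be captured for the duration of the study" and then gives the same start and end. Sections 7.3 and 7.4 label the Week 52 and Week 104 visits as End of Study visits. A woman who enters the extension continues to Week 104.

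Protocol Section 6.7 says that a woman of childbearing potential "must use one of the following contraceptive methods throughout the study and for at least 90 days after completing the study". The reason given is that the effects of the gel on the fetus are unknown. The reporting procedure that follows opens with "Should a female subject become pregnant or be suspected of being pregnant while participating in this study" and makes such a pregnancy reportable to the Medical Monitor. It adds: "Any pregnancy will be followed through delivery for the observation of any SAEs". It also says that a pregnancy is not in itself an AE or SAE.

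Section 8.1 leaves a passive route open: "AEs may also be reported spontaneously at any time". The SAE Reporting text under Section 8.4 starts the 24-hour clock when the site learns of an event. For a woman who stops early, Section 5.4 asks for final evaluations and describes no contact after them.

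SAP Section 3.7 defines a treatment-emergent AE as one starting on or after the day of first dosing. It gives no end.

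**The concern.** The protocol asks some women to avoid pregnancy for at least 90 days after the study, but sets no duty to report a pregnancy in that time and no contact that would find one. A pregnancy conceived shortly before the last urine test could also be missed by that test. It would have been exposed to the drug, and nothing scheduled afterwards would reveal it.

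New SAEs raise a related, weaker question. Women apply gel until the end of the 52-week phase they are in, so for a completer the reporting window shuts at about the last dose. The synopsis gives special attention to uterine, cardiovascular and thromboembolic events. One that begins in the following weeks reaches the database only if somebody volunteers it.

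Safety capture carries more weight in this trial than usual. Section 2.2 lists earlier exposure only up to 4 mg/day, against 8 mg/day here. After early termination, SAP Sections 3.3.2 and 3.8 plan no efficacy analysis and a brief report centred on safety and PK/PD.

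**Working it through.** The plan gives no figure to reproduce. The check compares time windows.

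**Inputs**
- AE and SAE window: first dose to Week 52, or Week 104 in the extension (Protocol 8.1, 8.4).
- Pregnancy-reporting duty: while participating; no week number and no period after the study (Protocol 6.7, reporting procedure).
- Contraception: at least 90 days after completing the study, women of childbearing potential only (Protocol 6.7).
- Last planned contact: the Week 52 or Week 104 visit (Protocol 7.3, 7.4, Appendix 1).
- Stated duration: up to 110 weeks per subject, with 2 weeks of screening (Protocol synopsis). Section 7.1 allows screening within 30 days.

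**1. Length of the interval without a planned contact**
- 90 days / 7 = 12.86 weeks.
- Leaving at Week 52: 52 + 12.86 = Week 64.9.
- Leaving at Week 104: 104 + 12.86 = Week 116.9.

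**2. Could the stated 110 weeks contain a follow-up period?**
- 2 + 52 + 52 = 106 weeks, and 110 − 106 = 4 weeks = 28 days. The synopsis does not explain them.
- If all 28 days were follow-up, 90 − 28 = 62 days would remain, and no contact is described in the 28.
- The 4 weeks need not be follow-up. With 30-day screening (30/7 = 4.29 weeks) and the 2-week window at the last visit, 4.29 + 104 + 2 = 110.3 weeks.

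**3. Position of each group after the last planned contact**
- *Completer without extension, or at the end of the extension.* The SAE window closes at about the last dose. The contraception period, where it applies, starts as the pregnancy-reporting duty lapses.
- *Extension entrant at Week 52.* No gap yet; collection continues to Week 104.
- *Early stopper.* On the words of 8.1 and 8.4 she stays inside the window until Week 52: a woman stopping at Week 20 has 52 − 20 = 32 weeks left. She has no scheduled contact in that time. The contraception period is counted from completing the study, so its start for her is not stated.
- *Woman unblinded for a safety emergency.* Section 6.1 ends her participation, and a duty worded on participation ends with it.

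**4. A late event that is volunteered**
The treatment-emergent definition has no end, so the event would be counted with the on-treatment events. An identical event that nobody volunteered would be absent. The limit lies in collection, and the SAP does not separate the two periods.

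**The case against.** Three inferences are tempting, and the documents do not support them.

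*That the protocol treats exposure risk as lasting 90 days.* It does not say so. Section 6.7 sets a contraception period for women of childbearing potential. It makes no statement about residual drug, thromboembolism or other SAEs. Neither document gives a half-life or washout time. The 90 days bear directly on pregnancy, and on SAEs only by analogy.

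*That later events go uncollected.* Section 8.1 accepts spontaneous reports at any time and requires the eCRF for every reported AE and SAE. The 24-hour SAE rule itself states no end date. Known AEs and SAEs are followed until resolved or stable, and known pregnancies through delivery. What is missing is active solicitation and a clear duty for new events.

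*That the safety comparison is biased.* The same window applies to both arms, and no event rate is given from which to derive an undercount. Entry runs to age 75 with a postmenopausal stratum, so the pregnancy point does not reach every woman.

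Two further objections have weight. Consent pages are not available here, so instructions to subjects about reporting after the study cannot be ruled out. The study has also stopped, so a prospective change may come too late for many women.

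The mismatch between the contraception period and the pregnancy-reporting duty survives all of this. The spontaneous route is worded for AEs, and Section 6.7 says a pregnancy is not one, so that route does not name an uncomplicated pregnancy. The follow-up rules help only once an event is known.

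**Conclusion.** The point holds in a limited form. For women of childbearing potential, a period of at least 90 days (12.9 weeks) that the protocol itself sets has no stated pregnancy-reporting duty and no planned contact. For completers, collection of new SAEs closes at about the last dose, with only a passive route after it. Early stoppers may remain nominally inside the window but have no scheduled contact after their final evaluations.

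The 90 days measure calendar time, not missed events. The documents do not allow an estimate of how many pregnancies or SAEs would be lost, nor a claim that any conclusion would change. The verdict assumes that completers apply gel until about the final visit, and that no follow-up contact is set out in a document not available here. It is an inexpensive improvement to safety capture, firmer for pregnancy than for SAEs.

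**What to change.** Reconcile Protocol Section 6.7 (contraception and pregnancy reporting) with Sections 8.1 and 8.4:

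- Extend the pregnancy-reporting duty to cover the protocol's own 90-day contraception period for women of childbearing potential, and state when that period starts for a woman who stops early.
- State a defined SAE reporting window after the last dose. Choosing 90 days would align the two windows, but the documents do not set that length for SAEs, so the sponsor should give a reason for whatever it chooses.
- Add one closing telephone contact in the existing call format, for completers and early stoppers, asking about SAEs and, where relevant, pregnancy.
- In SAP Section 3.7, flag these events as post-treatment and show them apart from on-treatment events.
- Update the stated study duration. With a 90-day window the longest participation is 2 + 104 + 12.86 = 118.9 weeks, against the stated 110.

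The cost is protocol and SAP wording, one call per woman and no clinic visit. The blinded-phase lock (Protocol 9.3) and the final lock could each move by up to 90 days for the last women.

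SAP Section 1.3 records early termination. Where the window has already passed, make a retrospective contact, or state in the safety report that new SAEs and pregnancies after the last visit were not actively sought.
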